9.2 Enrollment (Week 0)

All eligible participants will be enrolled into the study at Week 0 if they meet all entry criteria and have completed the screening procedures. Study procedures will not be repeated if the enrollment visit takes place within 5-10 business days of the screening visit. At this visit, staff members will:

- Assess eligibility (inclusion and exclusion criteria)
- Measure vitals (blood pressure, heart rate, respiratory rate, temperature), height and weight
- Obtain stool sample (if possible and not collected at Screening/Baseline) from subjects who have consented to stool collection
- Administer patient reported outcome questionnaires, which will include dietary questionnaires to measure *intake* of the food allergens and a food diary to assess baseline diet
- Completion of DSQ
- Assess concomitant medications and/or therapies

- Skin testing for allergies including prick and patch testing
- Randomize eligible participants to the 1FED or 6FED diet
- Provide standardized dietary instructions for 1FED or 6FED
- Research lab samples
 - Blood serum (~1-2 tsp, or 5-10 mL) for food IgE, CRD, and IgG4
 - Blood serum (~3-6 tsp, or 15-30 mL) for T cell studies

The participants will be encouraged to call the PI and/or study coordinator if they have any questions, concerns, adverse events, or changes in medication.

Stool samples may be collected from participants who have consented to stool collection at the Enrollment visit if they were unable to be obtained at the Screening/Baseline visit. Stool will only be collected at some, but not all, participating centers.

9.3 Phone Visits, Phase 1

A study staff member will conduct three phone visits (at weeks 1, 3, and 5) during Phase 1 in order to monitor participants' progress throughout the trial. The following procedures will occur during these phone visits:

- Assess con-med and/or con-therapy compliance
- Assess AEs
- Determine compliance with treatment
 - A dietary questionnaire to measure *intake* of the food allergens will be completed by the participants during weeks 1 and 5
 - A food diary will be completed by participants during weeks 1 and 5 to measure adherence
- Daily completion of the DSQ within the two weeks prior to the Phase 1 EOT EGD (Weeks 4 and 5)

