9.4 End of 1st Treatment phase or Early Withdrawal (Week 6)

For participants who have completed the 6 week Phase 1 or have withdrawn early from the study, the following procedures will occur:

- Measure vitals (blood pressure, heart rate, respiratory rate, temperature), height and weight
- Physical exam performed by a study clinician or qualified staff member
- Collect stool sample (if possible) from subjects who have consented to stool collection
- Administer patient reported outcome questionnaires
- Assess AEs
- Obtain up to 4 biopsies from the esophagus for research purposes (taken during SOC EGD)
 - One of these esophageal biopsies will be used for EDP
- Research lab samples
 - Blood serum (~1-2 tsp, or 5-10 mL) for food IgE, CRD, and IgG4
 - Blood serum (~3-6 tsp, or 15-30 mL) for T cell studies
 - Blood (6-10 mL) or saliva (1-2 mL) for future genetic testing may be collected at this visit (if not collected previously)
 - Blood for metabolomics (1 tsp, or 3-5 mL)
 - CBC with differential - if a CBC with differential was obtained clinically as part of standard of

care, obtain the results from the standard of care CBC

- Assess participant compliance with diet therapy and concomitant medications
- Pregnancy Test (urine)

Stool samples may be collected from participants who have consented to stool collection. Stool will only be collected at some, but not all, participating centers.

If a participant withdraws from the study before completing 6 weeks of dietary therapy, the end of treatment/early withdrawal visit should be conducted within one week of the participant's stopping dietary therapy. Participants should stay on their dietary therapy until results of biopsies are communicated to them.

Those participants who have resolution of their inflammation on endoscopy at the end of Phase 1 will complete the study at this time. Subjects with continued active inflammation will move on to phase 2, 6FED non-responders will start treatment with swallowed SGC (880mcg BID fluticasone propionate) and unrestricted diet and 1FED non-responders will start treatment of 6FED.

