13.3 Measures to Minimize Bias

Patients will be randomized using a 1:1 scheme to 1FED or 6FED within each investigative site. Study staff will remain blinded to the randomization plan so they do not know the upcoming treatment assignment will be for a patient until after the patient has been assigned. Study personnel who will perform the histologic assessments will be blinded to treatment assignment for the slides they are evaluating. The CRPC will not be told which diet a

participant has been assigned to, and they will not receive any information or documentation indicative of dietary assignment. The slides and/or images of slides provided to the CRPC will not contain any information that reveals which diet the participant is on. Knowledge of dietary assignment will be limited to study staff who need to know which diet a participant has been assigned to (i.e. dietitians).

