The instructions for the 1FED and 6FED therapeutic diets will be standardized across sites by providing consensus documents produced by registered dietitians who are experts in dietary elimination in EoE. There are currently no validated dietary questionnaires for measuring food allergen intake in adults in the US. Dietary intake and *consumption* of the allergens will be measured at the start of the trial and adherence to the dietary elimination (i.e. *avoidance* of the allergens) during the trial will be measured using modified versions of the NCI's usual dietary intake/diet history questionnaires and 3-day food diaries (<http://cancercontrol.cancer.gov>). Stool samples may be collected from subjects who consent to stool collection to evaluate the effect of diet on the microbiome.

Similarly, standardized instructions for using SGC will be provided, based on our prior studies. We have chosen to use fluticasone propionate (FP) rather than budesonide in this study, given our prior work in this area, and our recent finding that high-dose fluticasone is well tolerated and highly effective, and our preliminary findings concerning esophageal transcripts that predict responsiveness to FP therapy. The study design is shown schematically in Figure 1 Study Design Flowchart.

Figure 1 Study Design Flowchart

Analysis Populations

The analysis population for the primary and secondary endpoints will be the intent-to-treat population with the goal of including patients who have been randomized in the analyses. However, we will exclude patients who were inappropriately randomized and never completed the enrollment visit. Patients for which the primary endpoint of histological remission cannot be determined will be imputed as treatment failures. To maximize comparability with other studies, we will also perform per protocol analyses, including only individuals who complete the study phase of interest for all proposed studies.

Variables of Interest

Primary outcome:

- 1) Remission rate (<15 peak eosinophils/hpf)

Secondary outcomes:

- 1) Change in eosinophils/hpf from baseline to post treatment
- 2) Remission status: Patients will be classified into 3 remission categories: complete histological remission (≤ 1 peak eosinophils/hpf); partial remission (2-14 peak eosinophils/hpf); no remission (≥ 15 peak eosinophils/hpf)

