- 3) Histology Scoring System (HSS): Will include the overall score, grade score, stage score, and the inflammatory and structural sub-scores. Scores will be reported as distal, proximal, and maximum
- 4) HSS score by remission status (complete, partial, and no remission).
- 5) Endoscopy Scoring System (EREFS): Will include the overall score and the inflammatory and fibrostenotic sub-scores. Scores will be reported as distal, proximal, and maximal score.
- 6) EoE Diagnostic Panel (EDP): The summary EoE score (EDP total score) will be a secondary outcome.

Derived Variables.

- 1) HSS scores. Sum of the feature scores divided by the maximum possible score for the biopsy for grade and stage. The total score is the sum of the grade and stage scores. Inflammatory sub-scores include the following features: eosinophils, abscesses, surface layering, and surface necrosis. Structural sub-scores include basal layer hyperplasia, dilated intercellular spaces, apoptotic epithelia, and lamina propria fibrosis.
- 2) HSS remission. HSS remission is defined as a having both a grade and stage total score less than or equal to 3 and an eosinophil grade score no greater than 1. This is calculated separately for distal and proximal biopsies. When both distal and proximal biopsies are in remission, this is considered complete remission, when only one of the two biopsies meet these criteria, it is partial remission. When neither meet these criteria, it is no remission. Analyses will include full remission vs other and full+partial remission vs no remission.
- 3) EREFS. Total EREFS score will be calculated by summing the grades for all five of the features. The inflammatory score contained the sum of the exudate, edema, and furrows scores (this could range from 0 to 5), and the fibrostenotic score contained the sum of the rings and stricture scores (this could range from 0 to 4).
- 4) Adherence. Adherence will be dichotomized into mostly adherent vs not-mostly adherent. The judgement of adherence will be based on questionnaires about food intake and dietitian input. If inconsistent, food diaries will be reviewed. The final adherence call will be provided to the statistician.
- 5) Atopy. Atopy is a multi-faceted disease. Individuals will be defined as atopic if they report a history of asthma, eczema, allergic rhinitis, allergic conjunctivitis, IgE mediating food allergy

and/or atopic dermatitis.

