- 6) Time since diagnosis will be calculated as the study date at baseline minus the date at diagnosis.

Prior to any hypothesis testing, all variables will be reviewed for plausibility. Any values which are considered suspect will be reviewed by the clinical team to ensure accuracy. Continuous data will be evaluated for distributional assumptions of normality. Natural log-transformation will be considered for right skewed non-normally distributed data (the most typical skew seen in physiologic data).

Demographics/Patients Characteristics

Demographic, patient characteristics, medication use and study completion status will be summarized for the two treatment groups using median [interquartile range] for continuous variables and frequency and percentages for categorical variables. Treatment comparisons will be performed for demographics and patient characteristics using the Wilcoxon Rank sum test for continuous variables and the Fisher's Exact test for categorical variables. All tests will be conducted at $\alpha=0.05$.

Demographics and patient characteristics will be summarized within each Phase 1 treatment group between patients who choose to continue into Phase 2 and those who opt out. Any apparent difference will be noted.

Analysis of Primary Outcome

Primary Objective:

1. Determine the rate of remission following 1FED vs. 6FED and evaluate the relative efficacy of these dietary therapies.

Statistical hypothesis for the primary outcome:

H0: $p_{1FED} = p_{6FED}$

H1: $p_{1FED} \neq p_{6FED}$

where p_{1FED} =percentage of patients in histologic remission (<15 peak eosinophils/hpf) on the 1FED diet at end of Phase 1

p_{6FED} =percentage of patients in histologic remission (<15 peak eosinophils/hpf) on the 6FED diet at end of Phase 1

This hypothesis will be tested using the generalized linear mixed effects model with the logit link (for binary outcome) that accounts for the clustering within sites. Covariates to be considered in this model are sex, current age, baseline esophageal eosinophil count, adherence, presence of atopy, and time since diagnosis. All tests will be conducted at $\alpha=0.05$.

Analyses of Secondary Endpoint(s)/Outcome(s)

Following are the secondary objectives of the study:

- 1) To extend Phase 1 of this study with a prospective non-blinded trial that determines the rate of remission following SGC in the 6FED non-responders and the rate of remission following 6FED in the 1FED non-responders (Phase 2).

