- 2) To evaluate the effect of each therapy on histological remission defined by a variety of changes in eosinophils, including (a) pre- minus post-therapy peak eosinophil counts; (b) partial

remission (2-14 peak eosinophils/hpf); and (c) complete histological remission (≤ 1 peak eosinophils/hpf).

- 3) To evaluate the effect of each therapy by utilizing the histology scoring system (HSS) created to express the severity and extent of other abnormalities in the gastrointestinal (GI) tract that often accompany eosinophilic inflammation.
- 4) To evaluate endoscopic outcomes as assessed by the endoscopy scoring system (EREFS).
- 5) To determine the impact of each therapeutic intervention on biomarkers using the EoE Diagnostic Panel (EDP).

For secondary objectives 1, the remission rate at the 6-week time point for non-responders in Phase 1 who proceeded to Phase 2 will be summarized separately depending on the treatment patients received during Phase 1. The 95% two-sided confidence interval for the rate will be provided. If the remission rate is missing for patients that entered Phase 2, it will be imputed as a treatment failure.

To test hypotheses for each of the secondary objectives 2-5, treatment group comparisons at the end of Phase 1 will be performed using the generalized linear mixed effects model using the link that is appropriate for the endpoint (i.e. logit for binary, cumulative logit for ordered multinomial categories, identity for continuous). These models will account for the clustering within sites and will consider sex, baseline esophageal eosinophil count, adherence, presence of atopy, and time since diagnosis as covariates. For continuous data, appropriate transformations will be considered (e.g. log, square root, rank) to satisfy the assumptions of the analyses. If the remission status for the categorical outcomes is missing, we will evaluate how to treat the observation. If the study subject prematurely quit the clinical trial, then we will consider the observation a treatment failure. However, if the data was not captured (as in the case of a biopsy which did not capture both distal and proximal findings then we will consider imputation. Missing data for continuous outcomes may be imputed using multiple imputation techniques. Covariates for imputation will include investigative site, sex, presence of atopy and duration of disease. Secondary outcomes 2-5 will be tested at the two-sided $\alpha=0.01$ to account for multiple testing.

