Analyses of Exploratory Endpoint(s)/Outcome(s)

Exploratory Variables:

- 1) Change in Patient Reported Outcome (PRO) metrics (pre- minus post- treatment)
 - a. EoE Adult Symptom Score Activity Index (EESAI)
 - i. VDQ, AMS, Overall PRO
 - b. Adult EoE Quality of Life Score
 - i. Social impact, emotional impact, disease anxiety, eating/diet impact, choking anxiety
 - c. PROMIS General Health Questionnaire
- 2) Clinical parameters
 - a. Baseline disease activity measures (peak eosinophil count, EREFS, HSS)
 - b. Body mass index (BMI)
 - c. Presence of atopy and specific atopic diseases (e.g., is asthma associated with tx response/non-response)
 - d. Demographics (sex, age, race)
- 3) Biomarkers
 - a. Serum food specific IgE

- b. CRD – food specific components for IgE and IgG4
 - c. Serum food specific IgG4
 - d. EDP score
- 4) Skin testing results
- a. Skin prick tests to milk, egg, wheat, soy, peanut, shellfish, fish, and 5 tree nuts.
 - b. Positive is defined as ≥ 3 mm.
- 5) Milk driven T-cells
- a. T-cell count
 - b. Cytokine levels

Exploratory objectives are detailed below:

- 1) To evaluate the clinical and psychosocial effect of each therapy utilizing patient reported outcomes (PROs) to assess EoE symptoms and problems/feelings related to eating.
- 2) To evaluate factors predicting treatment response including
 - a) Clinical parameters
 - b) Serum food specific IgE, CRD, and IgG4
 - c) Skin testing results, in the form of prick and patch testing
 - d) Milk-driven T cells in blood

To test hypotheses for exploratory objective one, we will compare the treatment arms using general linear mixed models as described for the secondary outcome measures. To test hypotheses for exploratory objective 2, we will compare responders to non-responders using the generalized linear mixed effects model using the link that is appropriate for the endpoint (i.e. logit for binary, cumulative logit for ordered multinomial categories, identity for continuous). Covariates will be considered as appropriate. For continuous data, appropriate transformations will be considered (e.g. log, square root, rank) to satisfy the assumptions of the analyses.

Adverse Events

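### Dietary adherence, judged after open-label randomisation, is a candidate covariate in the SAP's primary and secondary models; if used, the arm term no longer tests the intent-to-treat hypothesis

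*SAP*

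**What the plan says.** The SAP sets the hypothesis p1FED = p6FED, remission percentages by assigned diet, in an intent-to-treat population. It tests this with a logistic mixed model that accounts for site (SAP, Analysis Populations; Analysis of Primary Outcome). On covariates it says "Covariates to be considered in this model are sex, current age, baseline esophageal eosinophil count, adherence, presence of atopy, and time since diagnosis".

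For secondary objectives 2–5 the models "will consider sex, baseline esophageal eosinophil count, adherence, presence of atopy, and time since diagnosis as covariates" (SAP, Analyses of Secondary Endpoint(s)/Outcome(s)). For the patient-reported outcomes, "we will compare the treatment arms using general linear mixed models as described for the secondary outcome measures" (SAP, Analyses of Exploratory Endpoint(s)/Outcome(s)). Nowhere does the SAP say what decides whether a listed covariate is used.

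Adherence is a two-level variable (SAP, Derived Variables, item 4): "The judgement of adherence will be based on questionnaires about food intake and dietitian input". The data come after randomisation. Protocol 9.3 states "A food diary will be completed by participants during weeks 1 and 5 to measure adherence", with intake questionnaires in the same weeks, and Protocol 9.4 adds at the end-of-phase or early-withdrawal visit "Assess participant compliance with diet therapy and concomitant medications". The trial is open label (Protocol 4.6), and Protocol 13.3 names dietitians among those who know the assigned diet.

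The protocol's own models are different. Sections 13.4.2 and 13.4.4 adjust only for sex/gender, atopy and disease duration. Section 13.4.3 adds an unadjusted chi-square test as a sensitivity analysis, which the SAP neither withdraws nor repeats.

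**The concern.** Adherence lies on the path from assigned diet to remission, and it is defined by the assigned diet: avoiding one food or avoiding six. A patient who cannot keep to six exclusions and stays inflamed is a failure of the 6FED assignment, and the intent-to-treat comparison counts that failure. Conditioning on adherence removes part of it. The arm coefficient then compares adherers with adherers and non-adherers with non-adherers. Those groups were not formed by randomisation, so the result is also open to any unmeasured cause shared by adherence and remission.

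If adherence differs by arm and adherers remit more often, similarly in both arms, the adjusted odds ratio is shifted in favour of the arm with lower adherence. Because the SAP only promises to consider the covariate, the choice between two different questions can be made after the data are seen, in a trial where most staff know the arm.

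**Working it through.** **1. The plan's own figure.** Protocol 13.6 assumes 45% against 70% remission, two-sided α = 0.05, and 60 per group for at least 80% power by a likelihood ratio test. The pooled normal approximation gives 61 per group, and 79.9% power at 60. Exact enumeration of the likelihood ratio test at 60 gives 80.6%. The figure reproduces, and it is a calculation for two proportions with no covariates.

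**2. Set-up for the null case.** From the protocol: 68 per arm, 1:1, two-sided 5%. Assumed, because the documents give nothing: true remission m = 42% in both arms (close to the protocol's 45% for 1FED), 1FED adherence 90%, and remission p_N in non-adherers of 10, 15 or 20% in both arms. Remission among adherers at adherence a then follows:

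p_A = [m − (1 − a)·p_N] / a

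With p_N = 15%:
- 1FED, a = 0.90: (0.42 − 0.015)/0.90 = 45.0%
- 6FED, a = 0.75: (0.42 − 0.0375)/0.75 = 51.0%
- 6FED, a = 0.65: (0.42 − 0.0525)/0.65 = 56.5%

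The diets are equal as assigned, yet within adherers 6FED looks better. At a = 0.75 the odds ratio among adherers is (0.51/0.49)/(0.45/0.55) = 1.27. Among non-adherers it is 1. The adjusted estimate lies between the two.

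**3. Rejection rates, equal true remission.** Mantel–Haenszel test stratified by adherence, 40,000 simulated trials per cell:

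| 6FED adherence | p_N 10% | p_N 15% | p_N 20% |
|---|---|---|---|
| 90% | 4.9% | 5.0% | 4.9% |
| 85% | 5.6% | 5.3% | 5.3% |
| 80% | 7.4% | 6.7% | 6.2% |
| 75% | 11.5% | 9.2% | 7.5% |
| 70% | 17.1% | 13.4% | 10.1% |
| 65% | 26.5% | 19.5% | 14.6% |

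The adjusted odds ratio is 1.00 with no gap, 1.12–1.19 at 10 points, 1.20–1.31 at 15 and 1.40–1.69 at 25. At 25 points with p_N = 15%, 19.4 of the 19.5 percentage points of rejections favour 6FED. The unadjusted chi-square stays at 4.5–4.9% throughout. A repeat run gave the same rates within simulation error.

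**4. A model closer to the SAP's.** Logistic mixed model with random site intercept (assumed 10 sites, site SD 0.3 on the logit scale), likelihood ratio test, p_N = 15%, 1,500 trials each:

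| 6FED adherence | With adherence | Median OR | Without adherence |
|---|---|---|---|
| 90% | 5.6% | 1.02 | 5.1% |
| 80% | 7.1% | 1.13 | 4.7% |
| 75% | 8.7% | 1.26 | 4.9% |
| 65% | 23.5% | 1.55 | 5.8% |

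The simulation standard error is about 0.6–0.7 points for the first three rows with adherence (√(0.056 × 0.944/1500) = 0.6) and about 1.1 for the last.

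**5. Sensitivity.**
- Reversed gap (6FED 90%; 1FED 80, 75 or 65%; p_N = 15%; logistic model without site): rejection 7.0, 9.2 and 19.7%, odds ratio 0.87, 0.80 and 0.65. The bias follows the lower-adherence arm.
- Null rate 45% instead of 42% (logistic model without site, p_N 10–20%, 4,000 trials): 6.2–7.6% at a 10-point gap and 12–20% at 20 points; arm-only model 4.3–4.9%.
- Weaker link (42% null, Mantel–Haenszel): p_N = 30% gives 5.8% at a 15-point gap and 8.0% at 25; p_N = 35% gives 5.2% and 5.8%.

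**6. Under the protocol's alternative.** At 45% against 70% with 60 per arm, the true odds ratio is (0.70/0.30)/(0.45/0.55) = 2.85, and the arm-only model returns a median of about 2.9. With adherence added at 90% on 1FED and 80% on 6FED, and p_N of 10–20%, the median becomes 4.5–5.5.

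**The case against.** The strongest reply is that listing a covariate for consideration is not using it, and that the protocol already supplies adherence-free comparisons: fixed baseline covariates for the primary model (13.4.2) and the unadjusted chi-square (13.4.3). Neither is withdrawn, so a reader holding both documents would have a valid intent-to-treat result. This stands as mitigation. It does not settle which result is primary. The SAP replaces the protocol's covariate list, the chi-square is only a sensitivity analysis, and the SAP itself states no intent-to-treat analysis of the primary endpoint that is certain to leave adherence out.

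The second reply concerns size. No passage gives adherence by arm or remission in non-adherers. The SAP's lower category may include partial avoiders, so a weak link with remission is plausible, and then even a 25-point gap does little. This also stands: any materiality threshold depends on the assumed link. The simulations also give every patient a known adherence value and ignore drop-out. The SAP counts undetermined outcomes as failures but has no rule for a missing adherence call, and dropping such patients from the model would bypass that imputation. The rates are illustrative.

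That dietitians know the diet adds little by itself, since adherence cannot be judged otherwise, and histology is read blind to arm. The extension to patient-reported outcomes is by cross-reference to exploratory analyses and carries little weight.

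**Conclusion.** The concern holds. The SAP admits a post-randomisation variable to models meant to test an intent-to-treat hypothesis, without an entry rule, and departs from the protocol's models in doing so. That follows from the text and needs no simulation.

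The size is conditional. With equal adherence, and the same adherence–remission relation in both arms, the test keeps its size. If non-adherers remit at 10–20%, a 5-point gap is negligible, a 10-point gap takes the 5% error to 6.2–7.4%, and the distortion becomes material from about 15 points (7.5–11.5%; 8.7% in the mixed model at 15% non-adherer remission). The 25-point case (14.6–26.5%) is the extreme of the assumed range. If non-adherers remit at 30–35%, inflation is slight throughout. The direction assumes a positive adherence–remission link, similar in both arms, with no unmeasured common cause. This should be fixed before analysis.

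**What to change.** - Delete adherence from the covariate lists for the primary and secondary models, and hence from the patient-reported outcome models that refer to them.
- Replace the wording about considering covariates with a fixed list of pre-randomisation variables, settled before data are seen. Either the protocol's three or the SAP's list without adherence would serve.
- Restate the protocol's unadjusted chi-square test in the SAP.
- Report any adherence-based analysis separately, labelled supplementary and non-randomised, with its own definition. The present per-protocol set cannot stand in for it: "we will also perform per protocol analyses, including only individuals who complete the study phase of interest" sets a completion criterion, not an adherence one.

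The cost is SAP wording. No new data are needed, and the chi-square test is already planned in the protocol.

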13.4.2 Primary Analysis of Primary Endpoint(s)/Outcome(s)

The primary endpoint for this study will be histologic remission (<15 eosinophils/hpf) determined at the end of Phase 1 and will be compared between the two treatment groups. The formal statistical hypothesis for the primary endpoint is:

$$H_0: p_{1FED} = p_{6FED}$$

$$H_1: p_{1FED} \neq p_{6FED}$$

where

p_{1FED} = percentage of patients in histologic remission (<15 eosinophils/hpf) on the 1FED diet at end of Phase 1

p_{6FED} = percentage of patients in histologic remission (<15 eosinophils/hpf) on the 6FED diet at end of Phase 1

This hypothesis will be tested using the generalized linear mixed effects model with the logit link (for binary outcome) that accounts for the clustering within sites. Important covariates to be included in this model are sex, presence of atopy and duration of disease. All tests will be conducted at $\alpha=0.05$.

The mixed effects model is planned in order to include the site as a random effect in the model. This approach assumes the sites included in this trial are representing a sample of sites about which we wish to make inferences and therefore will include site as a random effect instead of a fixed effect that implies we are only making inferences about those specific sites in the study.

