13.6 Sample Size Considerations

The sample size was based on the primary endpoint of the percent of patients in histologic remission (<15 eosinophils/hpf) at the end of Phase 1. Based on preliminary data, it is assumed that the remission rate for the 1FED population is 45%.¹⁶ We assume that the remission rate in the 6FED population will be increased to 70%. A sample size of 60 patients per group (120 total patients) will provide at least 80% power to detect a difference in rates between groups of 25% at the two-sided $\alpha=0.05$. This calculation is based on a likelihood ratio test statistic for comparing proportions. To allow for a potential approximate 15% drop-out, the sample size will be increased to 68 patients per group (136 total patients). This calculation was performed using the PASS vers. 12 software. The following table displays the robustness of the sample size under various response rate and drop-out rate scenarios.

Sample Size per group	Difference to detect with 80% power if 1FED rate is 45%	Difference to detect with 80% power if 1FED rate is 50%	Difference to detect with 80% power if 1FED rate is 55%
56	26%	24%	24%
60	25%	23.5%	23.5%
64	24%	23%	23%
68	24%	23%	22%

14.IDENTIFICATION AND ACCESS TO SOURCE DATA

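### The protocol fixes three covariates for the primary test; the SAP lists six for consideration with no selection rule, so the deciding model is not uniquely defined.

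*SAP*

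**What the plan says.** Protocol 13.4.2 specifies a logit mixed model with site as a random effect and closes the covariate list: "Important covariates to be included in this model are sex, presence of atopy and duration of disease". Protocol 13.4.3 then ranks the alternatives: the unadjusted chi-square test and a model with further covariates are sensitivity analyses.

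The SAP, under Analysis of Primary Outcome, keeps the same hypothesis, the same 0.05 level and the same type of model, with patients clustered by site: "This hypothesis will be tested using the generalized linear mixed effects model with the logit link (for binary outcome) that accounts for the clustering within" [...]. The covariate sentence changes: "Covariates to be considered in this model are sex, current age, baseline esophageal eosinophil count, adherence, presence of atopy, and time since diagnosis". Current age, baseline eosinophil count and adherence are new, and duration of disease has become time since diagnosis.

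The SAP gives no rule for entering or dropping a covariate. It does not carry over the ranking in Protocol 13.4.3, and it does not say that it supersedes the protocol on this point.

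**The concern.** A primary analysis should be defined so that two statisticians given the locked data would fit the same model. Here one could fit the protocol's three covariates and another all six, or any subset, and each could cite a study document.

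The SAP's verb is unlikely to be a slip for a fixed list. It uses the same verb for steps it clearly treats as optional, such as log-transforming skewed data and imputing partly missing biopsies. Where it means a fixed list, as for the imputation covariates, it says what the list will include. The same loosening appears in its secondary analyses, where the list also drops current age, so the SAP's own lists differ from each other.

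At stake is a borderline result: significant under one admissible model and not under another, with nothing written in advance to say which one counts.

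**Working it through.** **Inputs.** From Protocol 13.6: 45% remission on 1FED, 70% on 6FED, two-sided 0.05, 60 per group raised to 68 (136 in total). From Protocol 13.4.2 and the SAP: the two covariate lists. Assumed, because neither document gives them: covariate distributions and the strength of their association with remission.

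**1. The plan's own figure.** The protocol states: "A sample size of 60 patients per group (120 total patients) will provide at least 80% power to detect a difference in rates". With pooled rate (0.45 + 0.70)/2 = 0.575:

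n = [1.960·√(2·0.575·0.425) + 0.842·√(0.45·0.55 + 0.70·0.30)]² / 0.25² = (1.370 + 0.569)² / 0.0625 ≈ 60.2, so 61 per group.

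Power at 60 per group is 79.9% by this approximation and 80.6% by exact enumeration of the likelihood ratio test, which is the test the protocol names. The figure reproduces. It describes an unadjusted comparison and does not indicate which covariates belong in the model.

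**2. How many models the wording admits.** Six optional covariates give 2⁶ = 64 subsets. Leaving out adherence, which is measured after randomisation, the five baseline covariates give 2⁵ = 32, including the unadjusted model.

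**3. False-positive rate under no difference.** Logistic models without a site effect, 68 per arm, 57.5% remission in both arms, 3,000 trials per row. Effects are log odds ratios, per SD for continuous covariates and per level for sex and atopy.

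| Assumed effect of each covariate | Protocol's three | All five baseline | At least one of 32 below 0.05 |
|---|---|---|---|
| none | 4.8% | 4.9% | 6.2% |
| 0.3 | 5.0% | 5.1% | 8.4% |
| 0.5 | 5.3% | 5.0% | 9.6% |
| 0.8 | 4.7% | 5.7% | 13.4% |

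The Monte Carlo standard error is √(0.05·0.95/3000) = 0.4 points near 5%, and about 0.6 points in the last row.

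With other assumed effects, set per SD for every covariate, the last column was 6.6% (none), 8.1% (0.2 each), 8.5 to 9.0% (0.5 for baseline eosinophils) and 10.5% (0.4 each). Reporting whichever of only the protocol's model and the five-covariate model is significant gave 5.5 to 6.9%. Selecting covariates mechanically, by p<0.10 or by baseline imbalance, gave about 4 to 6%.

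**4. Agreement at 45% versus 70%.** With rising covariate strength, the protocol's model and the five-covariate model disagreed on significance in 2.0%, 3.2% and 5.2% of trials; across all runs the range was about 2 to 6%. The 32 models were not unanimous in 6.8%, 9.6% and 12.0%. Power for the five-covariate and protocol models was 84% and 84%, 86% and 85%, and 87% and 85%.

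**5. Adherence.** Assume adherence of 90% in one arm and 75% in the other, an odds ratio of 2.7 to 7.4 for remission given adherence, and equal overall remission. The full six-covariate model then rejects in 7.0 to 12.4% of trials. Fixing all six covariates would therefore make the model unique but would not protect the error rate.

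**The case against.** The SAP plans one hypothesis and one model. It does not authorise picking the model by its result, and Protocol 13.4.3 already places the unadjusted test among the sensitivity analyses. Biopsies are read by pathologists blinded to diet, and no interim efficacy analysis is planned. The simulation leaves out the site effect that both documents fix. Restoring the protocol's three covariates would define the test just as well. All of this stands. It limits the size of the problem, but it does not supply the missing definition.

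A reader might infer two stronger things.

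- **That the trial's family-wise error rate is about 8%.** The documents do not support this. No family of tests is planned, so the term does not fit, and 8% is only one point in a range set by assumed covariate effects and by always reporting the best of many models. For a choice between just two models, 8% would need their test statistics to correlate at about 0.77. In simulation the protocol's model and the full six-covariate model correlated at 0.87 to 0.99 when adherence was balanced.
- **That the SAP's baseline comparisons of the arms at 0.05 will drive covariate choice.** The SAP draws no such link. Protocol 13.4.6 plans the same comparisons alongside a fixed covariate set, and imbalance-driven selection did not inflate error in simulation.

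**Conclusion.** The point holds as a conflict between the two documents over the primary model and as an incomplete specification in the SAP. It does not show that the trial's error rate is inflated.

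Any single fixed model, or mechanical selection, keeps the false-positive rate near 5%. Outcome-driven choice among the 32 baseline models would raise it to roughly 7 to 11% for weak to moderate effects. It is slightly lower if no covariate is prognostic, and 13.4% in the stress case where every covariate has a log odds ratio of 0.8. These are ceilings, because they assume that the most favourable model is always the one reported. They rest on assumed covariate effects and a model without site.

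Under the design rates, the two most natural candidates give different answers in about 2 to 6% of trials. That is enough to justify settling the definition before outcomes are seen by arm.

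**What to change.** In the SAP, change *to be considered* to *will be included* and name one primary model: arm, site (random), sex, age, baseline peak eosinophil count, atopy and time since diagnosis, all entered regardless of significance or baseline balance. Then:

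- State the scale of each continuous covariate. The SAP's general allowance for log-transformation otherwise leaves the model open.
- State that adherence, being measured after randomisation, is not in the primary model.
- Label the protocol's three-covariate model and the unadjusted test as sensitivity analyses that do not decide the trial.
- Reconcile Protocol 13.4.2 with this, including duration of disease versus time since diagnosis.

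The five-covariate set is preferred because it uses a baseline count already collected, and its simulated power ranged from equal to about 3 points above the protocol's set. That margin depends on the assumed effects.

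The cost is that analysts lose the freedom to drop covariates, and the protocol needs a matching amendment (sponsor and IRB approval under Protocol 17.1) or a documented deviation. No new data are needed.
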